- A poster to display in pharmacists' work area that includes general information about PGx testing, eligible drugs (Table 1), and contact information for the testing laboratory, study pharmacist, and study coordinator.

B. Pharmacist Continuing Education

[figure not shown]
Continuing education (CE) courses on genetic testing and pharmacogenetics have been demonstrated to be an effective way to introduce new applications and even increase personal interest for providers (The Royal Society, 2005; Netzer & Biller-Andorno, 2004; Buchanan et al, 2002). Based on a survey of North Carolina pharmacists (Pro00062612), respondents prefer to learn about pharmacogenetics using a continuing education program, or online resources. Therefore, we will provide web-based seminars all participating pharmacists. For this study, participating pharmacists will be required to attend a CE session as described below. A second module on MTM will be required only of pharmacists in the MTM arm. All modules will be made available multiple times to accommodate pharmacists' schedules; pharmacists can receive CE credit. In addition, the slide decks will be made available throughout the study as a reference for pharmacists. The PGx CE presentation has been developed by the clinical pharmacist ([name]) on our team and has been used as a training module for pharmacists.

- In-person PGx CE & Study Overview (required of all pharmacists): The purpose of this CE is to provide an overview of basic genetic concepts and PGx-informed genomic medicine, including specific applications, highlighting many of the tests for the drugs listed in Table 1; to review test interpretation and sample test reports, strategies to effectively communicate PGx test results with both providers and patients, responses to possible patient questions, and documentation of results in the pharmacy record. The presentation will include an overview of a pharmacist "toolkit" that will be dispensed to each participating pharmacist. In addition, an overview of the study will also be presented, including the timeline, purpose/ significance, patient/pharmacist surveys, contact information of research team, and funding support. Pharmacists must attain an 80% score on a 5-question quiz at the end of the presentation in order to participate in the trial. Consent for pharmacist participation will also be obtained at this time (see section on Pharmacist Consent)

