Pharmacist Study Population. A total of 20 pharmacists working in independent community pharmacy settings in North Carolina who are members of the Community Pharmacist Pharmacogenetics Network (CPPN) will be eligible to participate in the cluster randomized trial. CPPN is a collection of community pharmacists in North Carolina who are currently offering or interested in offering PGx testing. Network members enroll with the understanding that they will be contacted regarding potential research studies. In addition, community pharmacies can be referred by CPPN members or contact the study investigator if interested in participating in the study. If additional recruitment is necessary, study staff will contact pharmacist using contact information provided via a mailing list from the North Carolina Board of Pharmacy. No prior experience with PGx testing is required. Pharmacies interested in participating in the MTM + PGx arm will be asked to confirm that they have obtained APhA training or will/have completed our in-person training module on MTM + PGx and have private space in the pharmacy to deliver MTM. If more than 10 pharmacies capable of offering MTM are interested in serving as a study site, we will randomly assign them to a study arm. For each pharmacy, we will request that a single pharmacist be assigned to the study. All pharmacists must participate in the PGx training session prior to patient enrollment and meet with the study pharmacist/study clinical coordinator to review the study protocol.

Patient Study Population. All patients seen by participating pharmacists will be eligible to participate in the study. Patients must be 18 years or older, able to consent to testing on their own

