The test results may be used to inform treatment decisions and also impact patient behavior regarding medication adherence. Potential negative consequences of testing for patients may include increased worry about one's health status and the health of relatives, negative emotional reactions, and familial implications. Study investigators will provide information to pharmacists regarding the Genetic Information Nondiscrimination Act (GINA) as part of the information in components of the toolkit; pharmacists will be encouraged to share this information with patients during discussion about testing.

Informed Consent for Pharmacists. Pharmacists will be invited to participate in the study and will be randomized to the MTM + PGx testing arm or PGx testing arm only. All participating pharmacists will be asked to provide informed consent by signing a study consent form that will be reviewed with them by the study pharmacist at the time of the provision of the CE and other educational materials (A consent form for pharmacists has been submitted for IRB review)

Informed Consent for Patients. Consent for testing will be obtained from patients as required by the testing company per standard clinical practice. Patient educational materials will be provided to facilitate discussion of testing with patients and informed decision-making. Pharmacists will be asked to disclose that this testing is being made available at no cost to the patient or their insurer as the pharmacy is participating in a research study looking at the delivery of these tests in a pharmacy setting that is supported by an NIH grant. The test itself is not under investigation and is offered by several major commercial clinical testing laboratories, therefore, a research consent is not required for testing (consent will be required for surveys, see Part III).

Incentive. Pharmacies in the PGx testing arm will receive a \$1,500 honorarium and pharmacies in the PGx + MTM testing arm will receive a slightly higher honorarium (\$2,000) given the additional effort required. Pharmacogenetic testing and MTM services will be provided at no cost to patients. Upon completion of the surveys (see next section), incentives will be offered to both pharmacist and patients.

PART III. SURVEYS

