medication supplied within the refill interval/# of days in refill interval). Patient-reported adherence data will be collected at baseline and 1 month following receipt of test results. The log record will be stored in a folder with the patient's name in the pharmacy; at the completion of the study, once the log record is returned to the research team, the log record will be coded and the folder will be destroyed so that the research team will have no patient identifier.

No identifying information will be collected on the patient logs. Forms will be kept in the pharmacy in a folder with the patient's name and any other relevant information noted by the pharmacist. At the completion of the study when the log is picked up by the research team, the folder will be discarded and all forms will be labeled with a study ID# number. A code will be established and accessible only to the clinical research coordinator and PI.

Pharmacist Surveys. Participating pharmacists will be asked to complete two surveys (Appendix 6). First, a baseline survey will be administered to all pharmacists prior to participation in the CE training. The baseline survey will assess knowledge of and experience with PGx testing, comfort with integrating PGx testing into pharmacy practice, comfort discussing PGx testing with patients, and experience with patient education and MTM. Pharmacist and pharmacy practice data will be collected including number of years in practice, other pharmacy services offered, and estimated time to complete each service. Second, we will administer a survey at the completion of the study to re-evaluate knowledge of PGx testing, comfort with integrating PGx testing into pharmacy practice, and comfort discussing PGx testing with patients. In addition, we will ask about the likelihood of adding PGx testing to their pharmacy services and major barriers to implementation including potential impact of adding this service on other currently offered services.

Table 2. Outline of proposed survey content for pharmacists and patients.

Pharmacists	Patients

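### The protocol does not say when pharmacies are randomised relative to pharmacist consent, baseline survey and quiz; its wording points to assignment before consent and quiz, with no rule for lost clusters and no balancing on prior PGx experience

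*Combined protocol and SAP*

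**What the plan says.** **Assignment.** PART II, Pharmacist Study Population, provides that if more than 10 MTM-capable pharmacies "are interested in serving as a study site, we will randomly assign them to a study arm". Informed Consent for Pharmacists states: "Pharmacists will be invited to participate in the study and will be randomized to the MTM + PGx testing arm or PGx testing arm only". It turns to the consent form in the sentence after that.

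**Consent and quiz.** PART I, section B, describes the PGx continuing education (CE) session required of everyone. Its final condition is "Pharmacists must attain an 80% score on a 5-question quiz at the end of the presentation in order to participate in the trial". On consent it adds: "Consent for pharmacist participation will also be obtained at this time (see section on Pharmacist Consent"). Informed Consent for Pharmacists agrees: the form is "reviewed with them by the study pharmacist at the time of the provision of the CE and other educational materials".

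**Baseline survey.** PART III, Pharmacist Surveys: "First, a baseline survey will be administered to all pharmacists prior to participation in the CE training". It covers prior experience with PGx testing and with MTM.

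**Operators.** Network members are pharmacists "who are currently offering or interested in offering PGx testing". Earlier PGx experience is not a requirement, and each pharmacy is asked to name one study pharmacist.

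**Differences between arms.** The MTM arm has two MTM sessions per patient, an additional training module (waived on proof of equivalent training) and a $2,000 honorarium against $1,500.

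**Analysis.** Survey Data Analysis names treatment as the fixed effect and cluster as a random effect. It names no pharmacy-level covariate.

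**The concern.** The pharmacy is the randomised unit. If a pharmacist learns the arm and only afterwards decides on consent, the decision can depend on the arm, because one arm asks for more work and more training and pays more. One pharmacist stands for one pharmacy, so a refusal can cost a cluster. If such losses differ between arms, the comparison is no longer between the groups that randomisation formed. The protocol has no retake, substitution, replacement or analysis rule for a pharmacy lost after assignment. The sensitivity analyses deal with individual dropout and missing data only.

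The second issue is balance. The primary outcome is whether the patient correctly recalls a result that the pharmacist explained, and how it is explained is left to the pharmacist. Experience with PGx testing is a plausible influence on that outcome. With only about 20 clusters, chance alone can leave the arms visibly unequal, and neither stratification nor adjustment is planned.

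**Working it through.** **1. The order of events, side by side**

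| Step | When | Section |
|---|---|---|
| Baseline survey | Before CE training | Pharmacist Surveys; PART III Pharmacist Study Population |
| Consent | At the PGx CE session | PART I section B; Informed Consent for Pharmacists |
| Quiz (80% of 5 = 4 correct) | End of that session | PART I section B |
| PGx training complete | Before patients are enrolled | PART II Pharmacist Study Population |
| MTM module | For those randomised to that arm | PART I section B |
| Randomisation | Tied to interest or invitation; no date | PART II Pharmacist Study Population; Informed Consent for Pharmacists |

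Two orderings are fixed: survey before CE (with consent and quiz), and randomisation before the MTM module. Randomisation can sit anywhere ahead of the MTM module. The recruitment and consent sections favour an early position, and nothing requires a late one.

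**2. The plan's own figure**

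20 pharmacies × 18 patients = 360, as stated. The power calculation behind 18 per pharmacy cannot be reproduced, because alpha, power, comprehension rates and intracluster correlation (ICC) are not given. A 10 v 10 split is implied by the rule about more than 10 pharmacies and by the target of 10 interviews per arm; it is not stated as an allocation ratio. Under it, one pharmacy is 18/180 = 10% of an arm.

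**3. Chance imbalance in prior PGx experience**

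Let K of the 20 pharmacies be experienced (K is assumed). Under simple 10 v 10 allocation, the number X in one arm is hypergeometric: P(X = x) = C(K, x) × C(20−K, 10−x) / C(20, 10), with C(20, 10) = 184,756. The arms differ by |2X − K|.

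- K = 4: 2 × 8,008 / 184,756 = 8.7% for a difference of 4 or more
- K = 6: 2 × (1,001 + 12,012) / 184,756 = 14.1%
- K = 8: 2 × (66 + 1,760 + 13,860) / 184,756 = 17.0%
- K = 10: 2 × (1 + 100 + 2,025 + 14,400) / 184,756 = 17.9% (7 v 3 or worse)

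Allocating all 20 at once within two experience strata would hold the difference to at most 1, and to 0 if K is even.

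**4. What a lost cluster costs (illustration; rates and ICC assumed)**

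Design effect = 1 + (18 − 1) × ICC. Effective n per arm = clusters × 18 / design effect. Power is that of a two-sided 5% two-proportion test with pooled variance under the null. Example, 60% v 75%, ICC 0.01, 10 v 10: design effect 1.17; n = 180/1.17 = 153.8; SE0 = √(0.675 × 0.325 × 2/153.8) = 0.0534; SE1 = √((0.24 + 0.1875)/153.8) = 0.0527; z = (0.15 − 1.96 × 0.0534)/0.0527 = 0.86; power 80.5%.

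| Assumption | 10 v 10 | 10 v 9 | 10 v 8 | 10 v 7 |
|---|---|---|---|---|
| 60% v 75%, ICC 0.01 | 80.5% | 78.2% | 75.5% | 72.0% |
| 60% v 80%, ICC 0.05 | 86.7% | 84.7% | 82.2% | 78.9% |
| 50% v 70%, ICC 0.05 | 81.8% | 79.6% | 76.9% | 73.5% |

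Each unreplaced loss costs about 2 to 4 points of power. Selection is a separate effect. If k of 10 pharmacies leave one arm and their comprehension would have been lower than the stayers' by d, the stayers' mean exceeds the full-arm mean by (k/10) × d. With k = 1 to 3 and d = 10 to 20 points (assumed), that is 1 to 6 points.

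**5. How often the quiz could remove a pharmacist (illustration)**

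With independent items, success rate p per item and no retake, P(fail) = 1 − [p⁵ + 5p⁴(1 − p)]. For p = 0.80, 0.90 and 0.95, expected failures among 20 are 5.3, 1.6 and 0.5.

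**The case against.** The strongest reply is that the sequence is inferred. No sentence dates randomisation. The phrase about interested sites may describe which pharmacies are randomised, not when, and the order of sentences in the consent section need not be chronological. Listing the common PGx session first and the MTM module second fits randomisation after the quiz equally well. Figure 1, the study overview, was not visible in the copy available and may show the sequence. This stands: a reader might conclude that the protocol definitely randomises before consent, survey and quiz, and the documents do not support that. The survey in particular comes before the CE session and could come before assignment.

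Other stronger readings also fail:

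- *Prior experience cannot be used for balance.* It could be asked when a pharmacy first shows interest, or taken from the survey as a covariate in the planned multivariate analyses. The defect is that neither is planned.
- *The quiz itself causes differential loss.* It follows a session given to both arms, so failure need not differ by arm. Refusal and withdrawal are the credible routes.
- *Each loss removes 10% of an arm for good.* A substitute pharmacist is not barred, and further pharmacies may be recruited. But substitution or replacement after the arm is known has no rule either.
- *A 7 v 3 split shifts the result by a known amount.* The shift is 0.4 × the operator effect, and the documents give no operator effect.

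It is also fair that chance imbalance is not bias, that common training and support narrow operator differences, and that a cluster random effect carries between-pharmacy variation into the standard error. The last holds only where that effect is retained: the plan drops it if it is not significant.

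**Conclusion.** The point holds as a gap with a likely unfavourable reading, not as a demonstrated error of sequence. The protocol leaves open whether pharmacies are assigned before consent and quiz, its wording leans towards before, and it has no rule for pharmacies lost after assignment. Because the arms differ in ways a pharmacist would care about, arm-dependent loss of clusters is a real possibility. How many would be lost cannot be known from the documents.

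The firmest figure is the chance of imbalance: a difference of 4 or more experienced pharmacies in about 9% to 18% of allocations. It assumes simple 10 v 10 allocation and 4 to 10 experienced pharmacies among 20. The power, selection and quiz figures rest on assumed inputs and show scale only.

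This is worth changing before any pharmacy learns its arm, because the order cannot be repaired afterwards.

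**What to change.** Amend PART II, Pharmacist Study Population, and align PART I section B and Informed Consent for Pharmacists with it:

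1. **Order.** Confirm MTM capability (private space, and MTM training held or willingness to take it). Then obtain pharmacist consent, complete the baseline survey, deliver the common PGx CE and apply the quiz. Only then randomise and disclose the arm. The MTM module follows for those allocated to it. MTM capability must be part of the entry check, because the protocol makes it a condition of that arm.
2. **Allocation.** Randomise these qualified, MTM-capable pharmacies 1:1, stratified by prior PGx testing (yes/no). At the least, include prior PGx testing as a pharmacy-level covariate in the primary model.
3. **Analysis.** Analyse every pharmacy in its assigned arm, and report by arm each pharmacy lost after assignment and the reason.

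The procedures before assignment mostly exist already; the stratified list and the reporting rule are new but short. The costs are that MTM training is booked after the CE session, that assignment waits until pharmacies qualify, and that pharmacies unable to offer MTM are not randomised.
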